#### **4.3 Management of Nivolumab-related infusion reactions**

Since Nivolumab contains only human immunoglobulin protein sequences, it has a low incidence of infusion or hypersensitivity reactions. However, if such a reaction were to occur, it might manifest with fever, chills, rigors, headache, rash, pruritus, arthralgias, hypotension, hypertension, bronchospasm, or other allergic-like reactions. All Grade 3 or 4 infusion reactions must be reported as an SAE if it meets the criteria. Infusion reactions must be graded according to NCI CTCAE (Version 4.0) guidelines.

Treatment recommendations are provided below:

For Grade 1 symptoms: (Mild reaction; infusion interruption not indicated; intervention not indicated).

- Remain at bedside and monitor subject until recovery from symptoms. The following prophylactic premedications are recommended for future infusions: diphenhydramine 50 mg (or equivalent) and/or acetaminophen/paracetamol 325 to 1000 mg at least 30 minutes before additional Nivolumab administrations.

For Grade 2 symptoms: (Moderate reaction requires therapy or infusion interruption but responds promptly to symptomatic treatment [eg, antihistamines, non-steroidal anti-inflammatory drugs, narcotics, corticosteroids, IV fluids]; prophylactic medications indicated for ≤ 24 hours).

- Stop the Nivolumab infusion, begin an IV infusion of normal saline, and treat the subject with diphenhydramine 50 mg IV (or equivalent) and/or acetaminophen/paracetamol 325 to 1000 mg; remain at bedside and monitor subject until resolution of symptoms. Corticosteroid therapy may also be administered as appropriate. If the infusion is interrupted, then restart the infusion at 50% of the original infusion rate when symptoms resolve; if no further complications ensue after 30 minutes, the rate may be increased to 100% of the original infusion rate. Monitor subject closely. If symptoms recur, then no further Nivolumab will be administered at that visit.
- For future infusions, the following prophylactic premedications are recommended: diphenhydramine 50 mg (or equivalent) and/or acetaminophen 325 to 1000 mg should be administered at least 30 minutes before Nivolumab infusions. If necessary, corticosteroids (up to 25 mg of SoluCortef or equivalent) may be used.

For Grade 3 or 4 symptoms: (Severe reaction, Grade 3: prolonged [ie, not rapidly responsive to symptomatic medication and/or brief interruption of infusion]; recurrence of symptoms following initial improvement; hospitalization indicated for other clinical sequelae [eg, renal impairment, pulmonary infiltrates]. Grade 4: Life-threatening; pressor or ventilatory support indicated).

- Immediately discontinue infusion of Nivolumab. Begin an IV infusion of normal saline and treat the subject as follows: Recommend bronchodilators, epinephrine 0.2 to 1 mg of a 1:1000 solution for subcutaneous administration or 0.1 to 0.25 mg of a 1:10,000 solution

injected slowly for IV administration, and/or diphenhydramine 50 mg IV with methylprednisolone 100 mg IV or equivalent), as needed. Subject must be monitored until the Investigator is comfortable that the symptoms will not recur. Nivolumab will be permanently discontinued. Investigators must follow their institutional guidelines for the treatment of anaphylaxis. Remain at bedside and monitor subject until recovery of the symptoms.

In case of late-occurring hypersensitivity symptoms (eg, appearance of a localized or generalized pruritus within 1 week after treatment), symptomatic treatment may be given (eg, oral antihistamine or corticosteroids).

#### **4.4 Duration of Therapy**

Arm D: Epigenetic therapy (azacitidine and entinostat) in combination with nivolumab will be given for six 28-day cycles on this protocol. Patients experiencing adverse event(s) that in the view of the treating physician or principal investigator make six cycles undesirable, may continue with Nivolumab as a single agent after only 2 cycles of concurrent epigenetic therapy with Nivolumab. Please see section 4.4.1 regarding treatment at time of progressive disease (PD).

Arm E and Arm F: Epigenetic therapy (azacitidine and entinostat) in combination with nivolumab will be given for six 28-day cycles on this protocol. Patients experiencing adverse event(s) that in the view of the treating physician or principal investigator make six cycles undesirable, may continue with Nivolumab as a single agent after only 2 cycles of concurrent epigenetic therapy with Nivolumab. Please see section 4.4.1 regarding treatment at time of progressive disease (PD).

Nivolumab monotherapy on all Arms may continue until one of the following criteria applies and at that time, nivolumab treatment will be permanently discontinued:

- Any Grade  $\geq 2$  drug-related uveitis, eye pain or blurred vision that does not respond to topical therapy and does not improve to Grade 1 severity within the re-treatment period OR requires systemic treatment
- Any Grade 3 non-skin, drug-related adverse event lasting  $> 7$  days, with the following exceptions for laboratory abnormalities, drug-related bronchospasm, hypersensitivity reactions, and infusion reaction:
  - Grade 3 drug-related bronchospasm, hypersensitivity reaction, or infusion reaction of any duration requires discontinuation
  - Grade 3 drug-related laboratory abnormalities do not require treatment discontinuation except:
    - Grade 3 drug-related thrombocytopenia  $> 7$  days or associated with bleeding requires discontinuation
    - Any drug-related liver function test (LFT) abnormality that meets the following

criteria require discontinuation:

- AST or ALT > 5-10x ULN for > 2 weeks
- AST or ALT > 10x ULN
- Total bilirubin > 5x ULN
- Concurrent AST or ALT > 3x ULN and total bilirubin > 2x ULN

- Any Grade 4 drug-related adverse event or laboratory abnormality, except for the following events which do not require discontinuation:
  - Grade 4 neutropenia  $\leq$  7 days
  - Grade 4 lymphopenia or leucopenia
  - Isolated Grade 4 electrolyte imbalances/abnormalities that are not associated with clinical sequelae and are corrected with supplementation/appropriate management within 72 hours of their onset
- Any dosing interruption lasting > 6 weeks with the following exceptions:
  - Dosing interruptions to allow for prolonged steroid tapers to manage drug-related adverse events are allowed after discussion with study PI.
  - Dosing interruptions > 6 weeks that occur for non-drug-related reasons may be allowed.
- Any adverse event, laboratory abnormality, or intercurrent illness which, in the judgment of the investigator, presents a substantial clinical risk to the subject with continued nivolumab dosing
- Confirmed disease progression at time points after first cycle of nivolumab monotherapy. This allows for patients to remain on treatment with nivolumab after disease progression if clinically stable. However, once the next disease assessment confirms progression or if clinically unstable, patients must stop treatment. (See section 4.4.1)
- Intercurrent illness that prevents further administration of treatment,
- Unacceptable adverse event(s), not able to be managed by steroid/or other immunosuppressive therapy (such as infliximab or IVIG) administration.
- Patient decides to withdraw from the study, or
- General or specific changes in the patient's condition render the patient unacceptable for further treatment in the judgment of the investigator.

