**IND 118,458 Sponsor: [name], M**

## SCHEMA

## Prior Study Population Immunotherapy Alone

- After a subject has completed 6 months of nivolumab (regardless of arm assignment), they can receive nivolumab every 4 weeks instead of every 2 weeks.

The goal of this study is to assess whether 6 cycles of concurrent epigenetic therapy consisting of azacitidine and entinostat in combination with nivolumab can increase response compared to nivolumab single agent in patients who are immunotherapy naïve (Arm D), or in patients whose disease has progressed on immunotherapy when compared to historical single agent docetaxel (Arms E & F).

Primary endpoint is the response rate by treatment Arm. Response will be assessed from first dose of trial therapy.

Patients experiencing significant toxicities on Arm D during cycles 1-6 of combination therapy of azacitidine, entinostat and Nivolumab may proceed to Nivolumab only. Otherwise, patients whose disease is responding, progressing, or stable on combination therapy with Nivolumab, azacitidine and entinostat will proceed to Nivolumab monotherapy after 6 cycles. Patients experiencing significant toxicities due to nivolumab or documented disease progression (see **Section 9**) on Arm E or Arm F during cycles 1-6 of combination therapy of azacitidine, entinostat and Nivolumab must come off study treatment. Patients whose disease is responding or stable on combination therapy with Nivolumab, azacitidine and entinostat will proceed to Nivolumab monotherapy after 6 cycles on Arms E and F.

We plan to enroll up to 20 patients each on Arms D, E and F (N=60). Allowing for up to 10% unevaluable patients, we will enroll up to 22 patients on each Arm (D-F), or a total of 66.

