## 2.4 Rationale for combining epigenetic therapy with immunotherapy

### 2.4.1 Clinical Rationale for combination epigenetic and immunotherapies

Due to 2015 FDA-approval of nivolumab in the 2nd line treatment setting of advanced or metastatic NSCLC, this protocol was previously amended to update nivolumab administration to be given concurrently starting at the initiation of combination study treatment. Therefore, for those patients randomized to combination therapy, nivolumab will be given in combination with epigenetic therapy for 6 cycles, followed by nivolumab monotherapy until disease progression. This will provide patients treated with maximal exposure to both epigenetic therapy and the immune checkpoint inhibitor, in keeping with standard of care practice. In this manner, patients will have longer exposure to the

potential benefits of both epigenetic therapy and immune checkpoint inhibition. This update in therapy is further supported by data indicating that 58.3% (14/24) patients were unable to receive two months of epigenetic therapy alone ("priming") prior to initiation of nivolumab in an earlier therapeutic intervention in this trial (Arm A), due to both symptoms (nausea, vomiting, fatigue, pain) and subsequent rapid disease progression on epigenetic therapy alone.

[figure not shown]
Importantly, the concurrent administration of epigenetic therapy and immune checkpoint inhibition is hypothesized to quickly combine the immune attraction signals from epigenetic therapy with the initial immune-tolerance inhibiting activity of immune checkpoint blockade, and allow the patient's tumor to be exposed to this interaction for a longer and perhaps more significant length of time than in the previous treatment arm. This is supported by pre-clinical data for the combination of these agents' mechanisms of action on efficacy and overall tolerability as detailed below.

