## 5.2 Nivolumab dose delay criteria

Nivolumab administration should be only delayed for the following immunologic toxicity:

- Any Grade  $\geq$  2 non-skin, drug-related adverse event, with the following exceptions:
  - Grade 2 drug-related fatigue or laboratory abnormalities do not require a treatment delay.
- Any Grade 3 skin, drug-related adverse event
- Any Grade 3 drug-related laboratory abnormality, with the following exceptions for lymphopenia, leucopenia, AST, ALT, or total bilirubin:
  - Grade 3 lymphopenia or leucopenia does not require dose delay.
  - If a subject has baseline AST, ALT, or total bilirubin within the Grade 1 toxicity range, delay dosing for drug-related Grade  $\geq$  3 toxicity.
- Any adverse event, laboratory abnormality, or intercurrent illness which, in the judgment of the investigator, warrants delaying the dose of study medication.

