##### 10.1.1.1 Arms/Regimens

All patients on each of the three arms will receive the same treatment of epigenetic therapy. The treatment consists of azacitidine 40 mg/m^2/day subcutaneously days 1-5 and 8-10 and entinostat 5 mg PO days 3 and 10 on a 28 day cycle concurrently with nivolumab for 6 cycles, followed by nivolumab until confirmed disease progression.

The arms are as follows:

Arm D: PD-1/PD-L1 naïve

Arm E: PD-1/PD-L1 refractory (i.e., previously treated with disease progression  $\leq$  24 weeks from first dose)

Arm F: PD-1/PD-L1 resistant (i.e., previously treated with disease progression  $>$  24 weeks from first dose).

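### Section 4.4 words its nivolumab permanent-stop list for monotherapy only, so in cycles 1–6 Arm D has few mandatory nivolumab stops and Arms E and F rely on an undefined term

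*Combined protocol and SAP*

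**What the plan says.** All three open arms receive azacitidine and entinostat "on a 28 day cycle concurrently with nivolumab for 6 cycles, followed by nivolumab until confirmed disease progression" (Section 10.1.1.1). Nivolumab exposure therefore starts on day 1 of cycle 1.

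The graded criteria for ending nivolumab permanently are in Section 4.4. They include drug-related Grade 3 non-skin events beyond 7 days and drug-related Grade 4 events, each with listed exceptions. The sentence that introduces them reads "Nivolumab monotherapy on all Arms may continue until one of the following criteria applies and at that time, nivolumab treatment will be permanently discontinued".

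For cycles 1–6 the plan speaks in three other places:

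- **Section 5.2**, which has no phase limit, opens its delay list with "Nivolumab administration should be only delayed for the following immunologic toxicity". Section 5.2.1 then says when dosing may resume.
- **The Schema** treats the arms differently. On Arm D, "Patients experiencing significant toxicities on Arm D during cycles 1-6 of combination therapy of azacitidine, entinostat and Nivolumab may proceed to Nivolumab only". On the other two arms the rule is mandatory: "Patients experiencing significant toxicities due to nivolumab or documented disease progression" … "on Arm E or Arm F during cycles 1-6 of combination therapy of azacitidine, entinostat and Nivolumab must come off study treatment".
- **Section 4.4** gives all three arms the same option. Patients whose adverse events make six cycles undesirable "may continue with Nivolumab as a single agent after only 2 cycles of concurrent epigenetic therapy with Nivolumab".

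**The concern.** Every patient starts in the three-drug phase. As worded, that phase has a weaker mandatory nivolumab stop than monotherapy does for the same event. Section 6.3 singles out pneumonitis as a particular concern and reports deaths from it, so re-exposure after a serious immune event is the practical risk.

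The wording may be a leftover. Section 2.4.2 describes an initial design of epigenetic priming followed by checkpoint monotherapy. Under that design a monotherapy lead-in would have covered all nivolumab dosing. Section 2.4.1 records that "this protocol was previously amended to update nivolumab administration to be given concurrently starting at the initiation of combination study treatment". That the lead-in was not updated at that point is an inference; the documents do not say so.

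Section 10.7 describes a multi-institutional study. Sites reading the same text could handle the same event differently.

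**Working it through.** No formula applies. The check takes one test event and asks of each toxicity rule whether it forces nivolumab to stop.

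**Test event:** a first nivolumab-related event in cycles 1–6, either Grade 4 (outside the 4.4 exceptions) or Grade 3 non-skin lasting more than 7 days, that resolves within 6 weeks.

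| Rule | Reach | Forces a nivolumab stop for the test event? |
|---|---|---|
| 4.4 graded list | Monotherapy, by its lead-in | Yes in monotherapy; not by its wording in cycles 1–6 |
| 4.3 infusion reactions | Any infusion | Only if the event is a Grade 3 or 4 infusion reaction |
| 4.6, Grade 3–4 toxicity | Any study treatment | No: it covers unresolved or recurrent toxicity, and this is a first event that resolves |
| 4.6, intolerable effects | Any study treatment | Only if the investigator so judges |
| 5, 4.6 and 5.2.1, delay over 6 weeks | Any phase | No: the event resolves sooner |
| 5.1.9, Grade 4 recurrence | Within the azacitidine/entinostat section | No: it needs a recurrence |
| 5.2, delay list | No phase limit | No: delay only |
| 5.2.1, resumption | No phase limit | Only for combined AST/ALT and bilirubin values; otherwise it permits resumption |
| Schema, Arm D | Cycles 1–6 | No: it permits a move to nivolumab alone |
| Schema, Arms E and F | Cycles 1–6 | Yes, if the toxicity counts as significant; no definition is given |
| 4.4 single-agent option | All arms, after 2 cycles | No: it permits nivolumab alone and does not exclude events caused by nivolumab |

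Section 4.2.5 sends diarrhea to an algorithm in the investigator's brochure. That may add a stop for colitis, but the algorithm is not in these documents.

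**Worked case:** Grade 3 pneumonitis that lasts more than 7 days and returns to baseline inside 6 weeks.

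- *In monotherapy, any arm:* permanent stop under 4.4.
- *In cycles 1–6, Arm D:* delay under 5.2. Section 5.2.1 requires pulmonary toxicity to return to baseline and then lets nivolumab resume.
- *In cycles 1–6, Arms E and F:* off treatment under the Schema if the event is called significant. Section 4.4 read alone would let the same patient continue nivolumab after 2 cycles.

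One limit applies on Arm D. A patient who moves to nivolumab alone while the event is still ongoing is then in monotherapy, and the 4.4 list applies. The gap concerns events that resolve before that switch, or before the three drugs resume.

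**Window:** 6 cycles × 28 days = 168 days (24 weeks). Two doses per cycle × 6 = 12 nivolumab doses for a patient who completes the phase. Enrollment is up to 22 patients per arm. This describes exposure, not the number of events.

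**The case against.** The strongest reply is that the list was plainly meant to be general. Section 5 sets its 6-week limit for every phase and points to 4.4 for exceptions. Section 4.6 does the same for all study treatment. Section 5.2.1 treats the 4.4 liver values as discontinuation parameters without naming a phase. Within 4.4, only the progression item repeats a monotherapy limit. Section 5.2 names Grade 3 but not Grade 4 skin events, which fits Grade 4 being handled by the 4.4 stop. This is good evidence of intent, and it stands. It does not supply the missing sentence: the cross-references bring in exceptions or single items, and none applies the graded list to cycles 1–6.

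A second reply is that *unresolved* in 4.6 has no time limit, so an event past 7 days could already qualify. That reading is possible. But 5.2.1 expects sites to wait for resolution and then allows dosing, and the reading does not reach a Grade 4 event that resolves quickly.

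Three stronger readings are tempting, and the documents do not support them:

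- *That on all arms, up to 66 patients, such an event requires at most a delay.* The Schema's removal rule covers Arms E and F, and 4.3, 5.2.1 and 4.6 supply stops on every arm.
- *That three of the four liver limits in 4.4 were deliberately left out of cycles 1–6.* The 5.2.1 bullet clarifies an exception to the resumption rules; it is not a selection of limits to import.
- *That the sponsor chose a laxer rule for the three-drug phase.* The cross-references point the other way.

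**Conclusion.** The point holds in a limited form and should be fixed. The clear gap is Arm D, up to 22 patients. For the test event in cycles 1–6, no graded rule there forces nivolumab to stop, apart from infusion reactions and combined liver values; beyond those, removal rests on the investigator's judgment. On Arms E and F the defect is different: a mandatory rule with an undefined trigger, alongside a 4.4 option that can give the opposite instruction.

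The number of patients affected cannot be estimated. The one overall figure, Grade 3–4 adverse events in 14% of patients on biweekly nivolumab (Section 2.2.3), is not split by relatedness, duration, timing or resolution.

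The conclusion assumes that sites follow the literal text and that the brochure algorithm, which is not available here, adds no general stop. Rapid reporting of serious events (6.5.1) and Safety Monitoring Committee review (6.6.4) add oversight but set no stopping criterion for an individual patient.

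**What to change.** 1. Reword the 4.4 lead-in along these lines: *In cycles 1–6 and in nivolumab monotherapy, nivolumab is stopped permanently if any of the following applies.* Keep the monotherapy wording of the progression item.
2. State that *drug-related* in that list means related to nivolumab, so that cytopenias attributed to azacitidine or entinostat follow the Section 5.1 table.
3. Define the Schema's Arm E/F trigger as an event that meets the 4.4 list. Limit the Arm D move to nivolumab alone, and the 4.4 single-agent option on all arms, to events that do not meet it.

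The same amendment should say whether Arm D patients may continue azacitidine and entinostat once nivolumab has stopped.

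**Cost:** a wording amendment, with no added visits or patients. A few patients who could now resume would stop instead. Those who stop before completing six cycles would count as not feasible under Sections 10.1.2 and 10.5, which moves an arm closer to its boundary (for example, 6 of 10 or 9 of 15). Events must also be attributed to an agent. Section 10.6 already plans to categorize toxicities separately for azacitidine/entinostat and for nivolumab, but Sections 6.4 and 6.5 attribute events to study treatment or study drug as a whole, so the adverse event form may need an extra field.

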#### **4.4.1 Treatment Beyond Disease Progression**

Treatment beyond disease progression is allowed for patients receiving concurrent azacitidine, entinostat and nivolumab on Arm D, Arm E and Arm F. If disease progression (PD) is noted during the 6 cycles of concurrent therapy per RECIST 1.1, the patient may continue study treatment until disease progression is confirmed. If at that time disease progression (PD) is confirmed, the patient will come off study treatment. After 6 concurrent cycles, patients will continue nivolumab monotherapy treatment irrespective of disease

progression status, and will follow the decision to treat beyond disease progression (PD) as per below. If the noted PD requires palliative radiation therapy, please see Section 4.2.12 regarding subsequent study treatment.

Subjects being currently treated with nivolumab monotherapy on any study Arm will be permitted to continue treatment beyond initial RECIST 1.1 defined PD as long as they meet the following criteria:

1. Investigator-assessed clinical benefit, and do not have rapid disease progression
2. Continue to meet all other study protocol eligibility criteria
3. Tolerance of the study drug
4. Stable performance status
5. Treatment beyond progression will not delay an imminent intervention to prevent serious complications of disease progression (e.g. CNS metastasis)

The decision to continue treatment beyond initial progression must be documented in the study records.

A radiographic assessment/scan will be performed at the end of the cycle following the original PD to determine whether there has been a decrease in the tumor size or continued PD. The assessment of clinical benefit should be balanced by clinical judgment as to whether the subject is clinically deteriorating and unlikely to receive any benefit from continued treatment with nivolumab.

If the investigator feels that the patient receiving nivolumab monotherapy continues to achieve clinical benefit by continuing treatment, the subject may remain on the trial and continue to receive monitoring according to the Study calendar.

New lesions are considered measurable at the time of initial progression if the longest diameter is at least 10mm (except for pathological lymph nodes which must have a short axis of at least 15 mm). Any new lesion considered non-measurable at the time of initial progression may become measurable and therefore included in the tumor burden volume if the longest diameter increases to at least 10 mm (except for pathological lymph nodes which must have a short axis of at least 15 mm).

For subject in either treatment arm, global deterioration of health status requiring discontinuation of treatment without objective evidence of disease progression at that time should be reported as symptomatic deterioration. Every effort should be made to document objective progression (i.e. radiographic confirmation) even after discontinuation of treatment.

